1.0 INTRODUCTION

1.1 Background and Rationale

1.1.1 Background

The Perclose ProGlide Suture-Mediated Closure System and the Perclose ProStyle Suture-Mediated Closure and Repair System (hereinafter referred to as Perclose SMC) is indicated for the percutaneous delivery of a suture for closing the common femoral artery and vein access sites of patients who have undergone diagnosis or interventional catheterization procedures. The devices can be used for access sites in the common femoral vein, 5F to 24 F sheaths, and the use of sheath sizes greater than 8F require at least two devices and the pre-close technique.

The vein indication was approved from the ProGlide Cohort of the Realism Clinical Trial. The prospectively planned retrospective analysis included patients in whom ProGlide SMC was used as the primary method for large bore venous access-site closure during the MitraClip procedure with a 24 F vascular sheath.

The MitraClip procedure requires single vein access with a 24 F vascular sheath. There are several interventional procedures using multiple vein access, such as atrial septal defect (ASD) closure and cardiac ablation.

The use of multiple catheters (sheaths) within the same vein is the standard practice of atrial septal defect (ASD) closure. Mahadevan et al. evaluated 65 ASD patients who underwent femoral vein closures with the ProGlide SMC and concluded that two ProGlide devices can be safely used at two different access sites in the same vein[1]. Hamid et al. reported the safety and effectiveness of vein closure, including 107 ASD closures with ProGlide [2]. Cardiac ablation is a procedure that can correct arrhythmias. Cardiac ablation uses multiple catheters for ablation, imaging (echo), and diagnosis (mapping), also pacing when appropriate. There is no standard practice in the selection of the access site of these catheters. Some prefer two access vessels (such as two sheaths from the left femoral vein and two from the right femoral vein), and some use a single vessel for all sheaths. When vein access is used for ablation (such as treatment of atrial fibrillation), manual compression is the most widely used method to achieve hemostasis after the sheath removal. However, manual compression is known to have frequent vessel complications and require more time for hemostasis and mobilization compared to vascular closure devices.

In these procedures, manual compression (MC) is the standard of care, and figure of 8 (Fo8) suturing technique is also used. Each sheath size of these procedures (4-15F) is smaller than the 24F sheath size used during the MitraClip procedure.

Abbott is aware that the current Instructions for Use contains the warning: "do not use the ProGlide SMC if there are multiple punctures since such punctures may result in a hematoma or retroperitoneal bleed". However, this warning is intended for multiple vessel punctures in a

single access site, not for multiple access sites in a single vein. Abbott believes vessel closure in multiple site access can be performed safely.

Abbott proposed to use 3 Abbott-funded real-world Investigator Sponsored Studies to evaluate the safety and effectiveness of the Perclose SMC for closure of multiple site access procedures such as cardiac ablation. The FDA accepted Abbott's proposal but also requested prospective duplex ultrasound (DUS) "sub-study" in which femoral DUS exams are performed in subjects undergoing atrial fibrillation or atrial flutter ablation procedures involving multiple femoral venous access sites per leg that are closed with the Perclose SMC to confirm the safety of the Perclose SMC in asymptomatic subjects.

1.1.2 Rationale for Conducting this Clinical Investigation

Femoral DUS is not routinely done in the standard practice of medicine and is typically in ablation procedures and other cardiovascular interventional procedures and only done when access site-related complications are visible (such as hematomas) and/or symptomatic. However, asymptomatic vascular complications are not always benign or insignificant. Therefore, this study will assess access site-related complications, including asymptomatic or non-visible, associated with multiple access site closures with the Perclose SMC by scheduled femoral DUS at discharge and at 30 days.

2.0 CLINICAL INVESTIGATION OVERVIEW

2.1 Clinical Investigation Objective

[figure not shown]
The objective of the study is to evaluate the safety of multiple access site closure in a single vein with the Perclose SMC by scheduled DUS at discharge and at 30 days (if vascular complications observed at discharge) in asymptomatic or non-visible subjects.

2.2 Devices Used in the Clinical Investigation

2.2.1 Name of the Device(s) Under Investigation

Devices used in this study are the commercially available Perclose ProGlide® Suture-Mediated Closure System and the Perclose Prostyle Suture-Mediated Closure and Repair System (Perclose SMC). The Perclose SMC is designed to deliver a single monofilament polypropylene suture to close femoral vessel access sites following diagnostic or interventional catheterization procedures.

Abbott will cover the cost of the study device/s for subjects who participate in the study. The study is an investigation using market released devices and device accountability is not required for this investigation.

2.2.2 Indication for Use

The Perclose SMC in this study will be used for **multiple access site closures in a single vein** in the ablation procedure. Either pre-close or post-close technique can be used per the site standard practice. The number of Perclose SMC to be used per access site should also be per site standard practice.

2.2.3 Description of the Device(s) Under Investigation

The Perclose SMC is market-released. The U.S. indication for use is the percutaneous delivery of suture for closing the common femoral artery and vein access site of patients who have undergone diagnostic or interventional catheterization procedures. The devices are under evaluation in this study for **multiple access site closure in a single vein**. The closure methodology for each access site is the same with the single access site closure. Please refer the Instruction for Use for more details.

3.0 CLINICAL INVESTIGATION DESIGN

This study is the prospective, single-arm, US multi-center, descriptive study to evaluate the safety of multiple access site closure in a single vein with the Perclose SMC. A total of 35 subjects will be registered at 2 US investigational sites. All subjects must have femoral DUS at discharge and at a 30-day follow-up visit (if any access site-related vascular complications (either symptomatic/visible or asymptomatic/nonvisible), nerve injury, or infection at discharge, by either the investigator or the core laboratory). All DUS images are assessed by the independent DUS core laboratory.

3.1 Clinical Investigation Procedures and Follow-up Schedule

The study flowchart is shown in **Figure 3-1**. A subject who is planned to have an ablation procedure and satisfies the eligibility criteria will be registered in this trial. Written informed consent must be obtained prior to the registration.

[figure not shown]
The ablation procedure and access site closure should be done per the site's standard practice. If the pre-close technique is used, the subject is considered to be registered in this study at the insertion of the 1st Perclose SMC into the body (in the case that the ablation procedure is not performed after pre-close by the Perclose, then the subject will be de-registered). If only the post-close technique is used, the subject is considered to be registered in this study at the insertion of the 1st Perclose SMC into the body after the ablation procedure.

3.2 Measures Taken to Avoid and Minimize Bias

The independent DUS core laboratory is used to assess DUS-detected vascular complications to avoid inter-site bias.

Study Name: Perclose Multi-Access DUS Trial

3.3 Early Termination of the Clinical Investigation

No formal statistical rule for early termination of the trial is defined. However, the Sponsor reserves the right to discontinue the study at any stage or reduce the follow-up period with suitable written notice to the investigator. Should the clinical investigation be discontinued by the Sponsor, the Principal Investigator or authorized designee will promptly inform the registered subjects at his/her site, if appropriate, and subjects will be followed per routine hospital practice.

A Principal Investigator, IRB, or regulatory authority may also suspend or prematurely terminate participation in the clinical investigation at the investigational site(s) for which they are responsible. The investigators will follow the requirements specified in the Clinical Trial Agreement.

4.0 ENDPOINTS

4.1 Primary Endpoints and Rationale

The primary endpoint of this study is:

• Vascular complications detected by scheduled DUS at discharge or 30 days in asymptomatic/non-visible complication subjects

In real-world practice, femoral DUS is not routinely done in ablation procedures and only done when access site-related complications are visible (such as hematomas) and/or symptomatic. Therefore, a scheduled femoral DUS in asymptomatic or non-visible complication subjects will support the overall safety of Perclose SMC in multiple access site closures in a single vein. Any visible and/or symptomatic access site-related complications will be also be captured but will be excluded from the primary endpoint analysis.

The primary endpoint is further categorized as major or minor. Major complications are defined as those which require surgical, interventional, or pre-specified repair and/or hospitalization. All other complications are considered to be minor complications.

Vascular access site-related complications include, but are not limited to:

- Femoral vein stenosis (> 50%) development at the puncture site related to closure technique
 - Requiring surgical or percutaneous repair (major)
 - Not requiring surgical or percutaneous repair
- Deep vein thrombosis in the target limb
 - Requiring surgical or percutaneous repair (major)
 - Not requiring surgical or percutaneous repair

Study Name: Perclose Multi-Access DUS Trial

- Venous bleeding, retroperitoneal bleeding
 - Requiring surgical or percutaneous repair (major)
 - o Not requiring surgical or percutaneous repair
- Venous access site injury including vessel laceration
 - Requiring surgical repair, angioplasty, stenting, ultrasound-guided compression, or thrombin injection (major)
 - Not requiring above
- Re-bleeding at the access site
 - Requiring treatment or re-hospitalization (major)
 - Not requiring treatment or re-hospitalization
- Hematoma
 - Hematoma \geq 6 cm
 - Requiring surgical or percutaneous repair (major)
 - Not requiring surgical or percutaneous repair
- Pseudoaneurysm
 - Requiring surgical or percutaneous repair (major)
 - Requiring thrombin injection, fibrin adhesive injection, or ultrasound-guided compression (major)
 - Not requiring above
- Arteriovenous (AV) fistula
- Venous tear
 - Requing surgical or percutaneous repair (major)
 - Not requiring surgical or percutaneous repair
- Venous perforation
 - Requiring surgical or percutaneous repair (major)
 - Not requiring surgical or percutaneous repair
- Arterial tear
 - Requiring surgical or percutaneous repair (major)
 - o Not requiring surgical or percutaneous repair
- Arterial perforation
 - Requiring surgical or percutaneous repair (major)
 - Not requiring surgical or percutaneous repair

• Other Complications found by DUS

DUS images will be analyzed by the independent DUS core laboratory and used for the primary endpoint analysis (**complications with bold face**). Investigators are also required to assess DUS detected complications, but the core laboratory is blinded to the site's assessment.

4.2 Descriptive Endpoints

Any vascular complications and access site complications will also be analyzed as the descriptive endpoints. Vascular complications include but are not limited to:

- Femoral vein stenosis (> 50%) development at the puncture site related to closure technique
- Deep vein thrombosis in the target limb
- Venous bleeding, retroperitoneal bleeding
- Venous access site injury including vessel laceration
- Re-bleeding at the access site
- Hematoma
- Pseudoaneurysm
- AV fistula
- Venous tear
- Venous perforation
- Arterial tear
- Arterial perforation
- Infection
 - requiring oral, intramuscular, or intravenous antibiotics, or leading to a prolonged hospitalization (major)
 - Not requring above (minor)
- Non-flow limiting suture material
- Access site-related nerve injury
 - Persisting for > 30 days (major)
 - Resolved \leq 30 days
- Pulmonary embolism

- Requiring surgical or endovascular intervention and/or resulting in death, to be confirmed by CT pulmonary angiography, lung ventilation/perfusion scan (VQ scan), or autopsy (major)
- \circ Not requring or resulting above
- Other (specify)

Procedural information listed below will also be analyzed.

- Procedure duration
- Type of Procedure (Cryo-ablation, RF ablation, etc.)
- Number of Femoral Vein Access Sites Per Subject
- Number of Femoral Vein Access Sites Per Leg
- Sheath Sizes Used
- Total Number of SMC used
- Number of SMC used per closure procedure
- Number of SMC used per access site
 - Number of SMC used for > 8F access site
- Number of SMC used per leg
- Device Success rate per access site
 - Successful hemostasis without surgical conversion, or additional non-study device (adjunctive manual compression and subcutaneous stitch are regarded as the standard of care and not included as failure)
- Anticoagulant and antiplatelet medications
- Use of protamine for heparin reversal

5.0 SUBJECT SELECTION AND WITHDRAWAL

5.1 Subject Population

This clinical study will register subjects of all genders who are planned to have elective ablation procedures requiring multiple vein access sites in a single femoral vein. Subjects must meet all eligibility criteria and provide written informed consent prior to registration in this study. Although complications are collected from all registered subjects, primary endpoint analysis is performed only in subjects with asymptomatic/non-visible complications, as the objective of this study is to understand asymptomatic/non-visible complications only observed by DUS.

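### Read literally, Section 5.1 limits the primary analysis to subjects who already have the endpoint event; 2.1, 4.1 and 5.1 need one at-risk denominator

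*Combined protocol and SAP*

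**What the plan says.** Section 5.1 collects complications from every registered subject, then says that "primary endpoint analysis is performed only in subjects with asymptomatic/non-visible complications", giving as its reason "as the objective of this study is to understand asymptomatic/non-visible complications only observed by DUS".

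Other sections describe the group differently:

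- **2.1** sets the objective as safety on scheduled duplex ultrasound (DUS) at discharge and, conditionally, at 30 days: "if vascular complications observed at discharge) in asymptomatic or non-visible subjects". Having a complication is not a condition for belonging to that group.
- **4.1** words the endpoint as "Vascular complications detected by scheduled DUS at discharge or 30 days in asymptomatic/non-visible complication subjects". Its rationale says that "a scheduled femoral DUS in asymptomatic or non-visible complication subjects will support the overall safety of Perclose SMC". A later sentence adds: "Any visible and/or symptomatic access site-related complications will be also be captured but will be excluded from the primary endpoint analysis".
- **1.1.1** gives the purpose of the requested sub-study as "to confirm the safety of the Perclose SMC in asymptomatic subjects", and **1.1.2** says that "this study will assess access site-related complications, including asymptomatic or non-visible".
- **6.4** requires a discharge DUS in every registered subject, and **15.0** describes the aim as confirming a frequency.

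Sections 3.0 and 5.6 plan 35 registered subjects. Sections 8.2, 8.6 and 8.7 make the study descriptive, with no hypothesis test and no success criterion. Section 4.2 also analyses all vascular and access-site complications descriptively. Section 8.1 (Analysis Population) has a heading but no readable text in the public copy.

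**The concern.** A frequency needs a denominator of subjects in whom the event could have been found, whether or not it was. Taken at its word, 5.1 admits only subjects in whom it was found. Counts by type and by major or minor category would survive, but a rate would not.

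This matters most in the favourable case. If the scheduled scans find nothing, the set defined by 5.1 is empty and yields neither a rate nor an upper limit, although a bounded low rate is the reassurance that the study is meant to supply. The primary endpoint is the study's main output, so its denominator should be fixed in one place before the data are seen.

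A second, smaller question sits in 4.1, which moves between restricting *subjects* (the bullet and rationale) and excluding *complications* (the later sentence). The two rules differ when one subject has both a visible complication and a separate finding seen only on DUS.

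**Working it through.** The readable text gives no expected rate, precision target or interval for the primary endpoint, so there is no planned figure to reproduce. The only input from the plan is n = 35 (3.0, 5.6). I assume that all 35 have an evaluable discharge DUS. Event counts, true rates and the reduced size of 30 are also my assumptions.

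**Step 1: the set as 5.1 words it.** Let x be the number of subjects with a DUS-only complication. Numerator and denominator are both x.
- x = 3: 3/3 = 100% (exact 95% CI 29.2% to 100%).
- x = 0: 0/0, undefined.

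For any x of 1 or more the rate is 100%, so it carries no information about frequency.

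**Step 2: an at-risk set.** Exact (Clopper-Pearson) 95% limits. For zero events the upper limit is 1 − 0.025^(1/n).
- 0/35: 1 − 0.025^(1/35) = 1 − 0.900 = 10.0%.
- 0/30 (five subjects assumed removed for visible complications): 1 − 0.025^(1/30) = 1 − 0.884 = 11.6%.
- 3/35 = 8.6% (1.8% to 23.1%).

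**Step 3: is zero events realistic?** With true rate p, the chance that none of 35 subjects has a finding is (1 − p)^35.
- p = 1%: 0.99^35 = 70%.
- p = 2%: 0.98^35 = 49%.
- p = 5%: 0.95^35 = 17%.
- p = 10%: 0.90^35 = 2.5%.

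So the undefined case is a plausible outcome if occult complications are uncommon.

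**Step 4: the sections side by side.**
- 5.1, literally: subjects who have an occult complication.
- 2.1: subjects without symptoms or visible signs, whatever the scan shows.
- 4.1 bullet: ambiguous. It can mean subjects who have such a complication, or subjects free of symptomatic or visible ones.
- 4.1 rationale: the same phrase describes the people who receive the scheduled scan, which favours the second meaning.
- 6.4 and 15.0: everyone is scanned and a frequency is wanted, which again favours the second meaning.

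The clear mismatch is between 5.1 and 2.1. That between 5.1 and 4.1 is softer, because the 4.1 bullet uses nearly the same phrase as 5.1.

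**Step 5: the subject with both kinds of complication.** Assume 3 subjects with an occult finding, 5 with a visible complication, and 1 of them in both groups.
- Restricting subjects: (3 − 1)/(35 − 5) = 2/30 = 6.7% (0.8% to 22.1%).
- Excluding only the visible complications: 3/35 = 8.6% (1.8% to 23.1%).

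The gap of 1.9 points is small against either interval. It shows the effect of the second question only and does not measure the circularity in 5.1.

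**The case against.** The strongest reply is that this is loose drafting whose intent is plain. The 5.1 sentence contrasts its group with all registered subjects and states its purpose; 1.1.1, 2.1, the 4.1 rationale, 6.4 and 15.0 all point to subjects without a symptomatic or visible complication. Section 8.1 may define exactly that set and may settle the overlap question too. The readable plan promises only descriptive analyses, not an upper confidence limit, and 4.2 reports every complication.

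Most of this stands, and it rules out three stronger readings that a reader might infer:

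- *That the primary analysis will be run on cases only, so the study cannot yield a rate.* The context favours an at-risk set, and the planned scans would support one.
- *That the plan has no analysis population.* Section 8.1 cannot be read in the public copy, so nothing can be concluded about its content.
- *That DUS findings in subjects with visible complications are lost.* They would still be reported under 4.2; the doubt is only whether they count in the primary endpoint.

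What the reply does not remove is the sentence itself. It is the most explicit readable statement of who enters the primary analysis, and it is wrong if followed. A sound 8.1 would leave 5.1 in conflict with it. Inferring the intent also leaves open how the overlap subject is counted.

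**Conclusion.** The point holds as a defect in a stated rule for the only primary endpoint: taken literally, 5.1 is circular, differs from 2.1 and does not fit 6.4 or 15.0. Confidence is high about that wording. It is lower about whether the denominator and the overlap rule are truly undefined, since 8.1 may settle both.

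The impact is modest. No error rate or success decision depends on it, and a usable rate can be derived from the planned data. Its clearest size is the zero-event case: no rate under 5.1 as written, against an exact 95% upper limit of 10.0% for 0/35, assuming all 35 scans are evaluable, or 11.6% for an assumed 0/30. It should be corrected because the correction is nearly free and fixes the denominator before results are known.

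**What to change.** Reword 5.1, and align 2.1, 4.1 and 8.1, to one at-risk denominator that does not depend on the DUS result. If 8.1 already contains a sound definition, carry that through. Otherwise, for example:

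- **Denominator:** registered subjects with an evaluable discharge DUS and no symptomatic or visible access-site complication at the discharge assessment. Fixing that status at discharge keeps in the set a subject with an occult discharge finding who later becomes symptomatic; otherwise membership would depend on a later outcome.
- **Numerator:** those with a core-laboratory DUS-detected complication at discharge or 30 days.
- **Overlap:** state how a subject with both a visible complication and a separate DUS-only finding is counted.
- **Supporting line:** report DUS-only findings over all registered subjects with an evaluable discharge DUS, with an exact 95% CI.

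The cost is wording in these sections and one extra line in the results table. No subjects, scans or data items are added.

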5.2 Subject Recruitment/Screening and Informed Consent

5.2.1 Subject Recruitment and Screening

Subjects admitted for an ablation procedure must be screened for the clinical study.

Subjects meeting the inclusion criteria and none of the exclusion criteria will be informed about the clinical study and asked to sign an informed consent. As the study-specific procedure is limited to femoral DUS at discharge and at 30 days, each site should follow their site standard practice for baseline information collection, the ablation procedure, and access site closures with the Perclose SMC, as well as the subject management.

5.2.2 Informed Consent

The Investigator or his/her authorized designee (if applicable) will conduct the Informed Consent process, as required by applicable regulations and the center's IRB. This process will include a verbal discussion with the patient on all aspects of the clinical investigation that are relevant to the patient's decision to participate, such as details of clinical investigation procedures, anticipated benefits, and potential risks of clinical investigation participation. Sites must inform patients about their right to withdraw from the clinical investigation at any time and for any reason without sanction, penalty, or loss of benefits to which the patient is otherwise entitled. Withdrawal from the clinical investigation will not jeopardize their future medical care or relationship with the investigator.

During the discussion, the Principal Investigator or his/her authorized designee will avoid any improper influence on the patient and will respect patient's legal rights. Financial incentives will not be given to patients. Patients may be compensated for time and travel directly related to the participation in the clinical investigation. The site shall provide the patient with the Informed Consent form (ICF) written in a language that is understandable to the patient and that has been approved by the center's IRB. The patient shall have adequate time to review, ask questions, and consider participation. The Principal Investigator or his/her authorized designee will make efforts to ensure that the patient understands the information provided. If the patient agrees to participate, they must sign and date the Informed Consent form, along with the person obtaining the consent prior to any clinical investigation-specific procedures. The site will file the signed original in the patient's hospital or research charts, and provide a copy to the patient.

Sites should report any failure to obtain informed consent from a patient to the Sponsor within 5 working days and to the reviewing center's IRB according to the IRB's reporting requirements.

If, during the clinical investigation, new information becomes available that can significantly affect a subject's future health and medical care, the Principal Investigator or his/her authorized designee (if applicable) will provide this information to the subject. If relevant, sites will ask the subject to confirm their continuing informed consent in writing.

In addition, sites must obtain an authorization for use and disclosure of the subject's protected health information, in accordance with the Health Insurance Portability and Accountability Act (HIPAA), from the subject or their legally acceptable representative.

